### **7.3. Selection of Doses in the Study**

PH94B is an investigational new drug that has shown statistically significant efficacy, rapid onset of effect, and an excellent safety profile in the treatment of performance anxiety and social

interaction anxiety in subjects diagnosed with SAD. A [REDACTED] formulation has been used i.n. in Phase 1 and Phase 2 clinical studies. The i.n. route of administration is required for the small quantities of PH94B to engage directly with nasal chemosensory neurons interspersed in the nasal olfactory epithelium.

Nonclinical and clinical studies with PH94B are summarized in the IB. Nonclinical studies on chronic exposure to PH94B and clinical Phase 2 studies have shown that PH94B is safe for use in human subjects [REDACTED]. PH94B could not be quantified in blood samples of human subjects administered [REDACTED] i.n. in a Phase 1 study. No SAEs associated with the administration of PH94B have been observed in any clinical study to date. Safety margin based no-observed-adverse-effect levels for toxicity have indicated that the proposed doses are safe. The profile of physiological and behavioral responses to PH94B was similar for males and females, but the magnitude of effect is slightly reduced for males at the 1.6- $\mu$ g dose. Based on Phase 1 and Phase 2 study outcomes after a single dose of PH94B of 3.2  $\mu$ g (one 1.6- $\mu$ g spray per nostril) and observations made in study PH94B-CL019, this study proposes the self-administration of repeat dosing of PH94B 3.2  $\mu$ g (one 1.6- $\mu$ g spray per nostril), for males and females. PH94B, the investigational product (IP), will be self-administered i.n. up to 4 times per day in an open-label study. The objective of the study is to evaluate the safety and tolerability of PH94B use, and incidence of AEs in subjects with SAD over a 12-month observation period. Monthly clinic-based visits will be used to monitor subjects throughout the course of the study.

#### 7.4. Study Sites

The study is designed as a multicenter study conducted in the USA with approximately 40 clinical study sites.

#### 7.5. End of Study Definition

A clinical study is considered completed when the last subject's last study visit has occurred.

## 8. SUBJECT POPULATION

### 8.1. Selection of Study Population

Eligibility for participation in the study will be determined from demographic information, medical and psychiatric history, physical and psychiatric examination, 12-lead ECG, clinical laboratory findings, and clinical rating scale assessments.

Any information to be disseminated to potential subjects (handouts, brochures, etc.), as well as direct advertisements (including direct electronic or digital advertising), must be approved by VistaGen and by the appropriate IRB prior to use and implementation.

### 8.2. Study Entry Criteria

Subjects who do not meet all of the eligibility criteria will not be enrolled.

#### 8.2.1 Inclusion Criteria

To be considered eligible to participate in the study, all subjects must meet the following inclusion criteria:

1. Subject must have participated in a previous PH94B SAD study.  
Note: Subjects who have not participated in a prior PH94B SAD study may be permitted to enroll following approval by the sponsor on a case-by-case basis.
2. Written informed consent provided prior to conducting any study-specific assessment.
3. Male and female adults, 18 through 65 years of age, inclusive.
4. Women of childbearing potential must be able to commit to the consistent and correct use of an effective method of birth control throughout the study and must also have a negative urine pregnancy test result at both Screening (Visit 1) (for subjects who attend Visit 1) and Baseline (Visit 2), prior to IP administration. Effective methods of contraception include: condoms with spermicide, diaphragm with spermicide, hormonal contraceptive agents (oral, transdermal, or injectable), or implantable contraceptive devices.
5. Current diagnosis of SAD as defined in the Diagnostic and Statistical Manual of Mental Disorders, 5th Edition, and confirmed by the Mini-International Neuropsychiatric Interview (MINI).
6. Clinician-rated HAM-D17 total score < 18 at study entry (Screening [Visit 1] or Visit 2 [Baseline] as applicable).
7. Negative COVID-19 test for subjects with COVID-19 symptoms or those who had direct exposure to someone with a positive COVID-19 test, and/or completion of quarantine period consistent with requirements at the study site as determined by the investigator.

#### 8.2.2 Exclusion Criteria

To be considered eligible for entry into the study, a subject must not meet any of the following exclusion criteria at study entry.

1. Any history of bipolar disorder (I or II), schizophrenia, schizoaffective disorder, psychosis, anorexia or bulimia, premenstrual dysphoric disorder, autism-spectrum disorder, obsessive-compulsive disorder, or treatment-refractory major depressive disorder.

Any other current Axis I disorder, other than SAD, which is the primary focus of treatment. Note that subjects with concurrent Generalized Anxiety Disorder are eligible for the study provided that Generalized Anxiety Disorder is not the primary diagnosis.

2. In the opinion of the Investigator, the subject has a significant risk for suicidal behavior during the course of their participation in the study, or
  - a. At Screening (for subjects who attend Visit 1): the subject scores “yes” on items 4 or 5 in the Suicidal Ideation section of the Columbia-Suicide Severity Rating Scale (C-SSRS) with reference to a 6-month period prior to screening; or
  - b. At Screening (for subjects who attend Visit 1): the subject has had 1 or more suicidal attempts with reference to a 2-year period prior to screening; or
  - c. At Baseline (Visit 2): the subject scores “yes” on items 4 or 5 in the Suicidal Ideation section of the C-SSRS with reference to last visit; or
  - d. The subject is considered to be an imminent danger to themselves or others.
3. Subjects using the following psychotropic medications at enrollment or within 30 days before study entry: antidepressants (including monoamine oxidase [MAO] inhibitors), anxiolytics, stimulants, anticonvulsants, mood stabilizers, antipsychotic medications, gabapentin, pregabalin, opioids, naltrexone, esketamine, and ketamine. Eszopiclone, ramelteon, melatonin, zaleplon, zolpidem, or anti-histamines prescribed for insomnia are allowed.
4. Use of benzodiazepines or unapproved treatments such as beta blockers, within 30 days before study entry and during the study. Use of beta blockers for treatment of hypertension or cardiac conditions is allowed. Subjects who have been taking benzodiazepines daily for 1 month or longer at the time of Visit 1 are not eligible to participate.
5. Use of any over-the-counter product or herbal preparation for treatment of the symptoms of anxiety or social anxiety within 30 days before study entry; concomitant use is prohibited during the study.
6. Clinically significant nasal pathology or history of significant nasal trauma, nasal surgery, total anosmia, or nasal septum perforation that may have damaged the nasal chemosensory epithelium.
7. Subjects who meet criteria for moderate or severe alcohol or substance use disorder within the 1 year prior to entry into the study.
8. Subjects with a positive urine drug screen at study entry [REDACTED].
9. An acute or chronic condition, including an infectious illness, uncontrolled seasonal allergies at the time of the study, or significant nasal congestion that potentially could affect drug delivery to the nasal chemosensory epithelium.
10. Any current clinically significant and/or uncontrolled medical condition, based on medical history or as evidenced in screening assessments, such as COVID-19, HIV, cancer, stroke, congestive heart failure, uncontrolled diabetes mellitus, or any other medical condition or disease that, in the clinical judgment of the Investigator, could place the subject at undue risk, interfere with study participation, or confound the results of the study.

11. Women who have a positive urine pregnancy test prior to IP administration. Women who are currently breastfeeding are not eligible.
12. History of cancer or malignant tumor not in remission for at least 2 years. Basal cell skin cancers are not exclusionary.
13. Subjects with clinically significant abnormalities in hematology, blood chemistry, urinalysis, 12-lead ECG, or physical examination identified at study entry or during the legacy study which, in the clinical judgment of the Investigator, could place the subject at undue risk, interfere with study participation, or confound the results of the study.

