**For the purposes of enrollment, these subjects are referred to as “Completers”.**

- While these subjects enter the long-term safety study at Visit 2, Investigators must transcribe the following screening data (Visit 1) from the antecedent study to the present long-term safety study: demographics, the MINI, medical and psychiatric history, and the SAD Diagnostic Criteria checklist. If there have been any changes, these details should be updated. This data from the antecedent study must be re-entered into the [Visit 1 eCRF](#) for the present study. All other assessments scheduled for Visit 2 must be performed as indicated in the schedule of events (see [Table 2-1](#)).
- If the subject enters the present study on the same day as the last visit of their antecedent study, results from the assessments on that day may be used to enter data into the eCRFs for the antecedent study and for Visit 2 of the present study without repeating them.
  - For example, [REDACTED] assessment completed for the last visit of the antecedent study may be transcribed for this long-term safety study provided that the last visit occurred on the same day as Visit 2 for the present study. Details on preparing a certified copy of the results will be provided in the eCRF completion guidelines.

- For clinical laboratory assessments, 2 sets of blood and urine samples should be obtained and sent to the lab for analysis: one for the antecedent study and one for the long-term study. Note that these can be collected at the same time to avoid unnecessary needlesticks.

Subjects who have not participated in a prior PH94B SAD study may be permitted to enroll following approval by the sponsor on a case-by-case basis. For the purposes of enrollment, these subjects are referred to as “New Subjects”.

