#### **10.3.1.2.4 Columbia-Suicide Severity Rating Scale**

The C-SSRS is a semi-structured interview that captures the occurrence, severity, and frequency of suicide-related thoughts and behaviors during the assessment period. The interview includes definitions and suggested questions to solicit the type of information needed to determine if a suicide-related thought or behavior has occurred. The C-SSRS has a “baseline” version which will be completed at Screening and a “Since Last Visit” version that will be completed at all subsequent visits. There are a maximum of 19 items to be completed: 7 that are required, 10 potential additional items if there is a positive response to a required item, and 2 items for suicide/suicide behavior present during the interview. The C-SSRS uses dichotomous scales (i.e., yes or no), Likert scales, and text or narrative to further describe the thoughts or behaviors.

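### The objective suicidality exclusions differ by entry route, and none uses suicidal behaviour at Visit 2, so some attempts are left to judgement clauses alone

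*Protocol*

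**What the plan says.** Exclusion 2 in Protocol 8.2.2, with the same wording in the synopsis, has an opening clause and four parts.

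- **Opening clause:** "In the opinion of the Investigator, the subject has a significant risk for suicidal behavior during the course of their participation in the study". It carries no visit, entry route or look-back limit.
- **2a:** a yes on C-SSRS ideation item 4 or 5 at Screening, for Visit 1 attendees, "with reference to a 6-month period prior to screening".
- **2b:** at Screening, for Visit 1 attendees, "the subject has had 1 or more suicidal attempts with reference to a 2-year period prior to screening".
- **2c:** at Visit 2, a yes on "items 4 or 5 in the Suicidal Ideation section of the C-SSRS with reference to last visit".
- **2d:** imminent danger to self or others, again with no visit or route limit.

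Under Section 7.1, subjects within 14 days of finishing their antecedent study enter at Visit 2. Those further out attend Visit 1 first, and Section 10.2.1.1 sets 7 to 35 days between the two visits.

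Section 10.3.1.2.4 says the C-SSRS "captures the occurrence, severity, and frequency of suicide-related thoughts and behaviors during the assessment period". It is given in its since-last-visit form at Visit 2.

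For direct entrants, Section 10 says "Investigators must transcribe the following screening data (Visit 1) from the antecedent study". The list is demographics, the MINI, medical and psychiatric history, and the SAD diagnostic checklist. The C-SSRS is not on it.

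Section 10.2.2.1 puts the review of entry criteria in the first group of Visit 2 procedures. The C-SSRS is in a second group, reserved for subjects who have already passed all criteria.

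**The concern.** The protocol makes attempts (2b) and ideation (2a) separate grounds for exclusion at screening, so it does not itself treat ideation as a stand-in for behaviour. At Visit 2 the attempt ground disappears, although the interview done that day collects the information. For direct entrants it never appears.

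Three things are at stake.

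- **Subject safety:** for screened subjects, the attempts closest to first dose are the ones that no objective rule reaches.
- **Consistency:** the same history meets a fixed rule on one route and a judgement on the other, and no reason is given for the difference.
- **Interpretation:** suicidality is part of the primary objective (Protocol 6.1). SAP 6.1.1 takes the C-SSRS baseline from the Visit 1 version, which direct entrants do not complete in this study and which Section 10 does not transcribe. The omission from the transcription list therefore touches the analysis as well as eligibility.

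**Working it through.** No arithmetic applies. The check maps each objective rule against the entry route and the timing of an attempt.

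| Case | Route | Timing of attempt | 2b | 2c | Objective exclusion? |
|---|---|---|---|---|---|
| 1 | Visit 1 first (more than 14 days out) | Within 2 years before screening, including between the studies | Met | Not needed | Yes |
| 2 | Visit 1 first | Between Visit 1 and Visit 2 (7 to 35 days) | Window has closed | Ideation only | No |
| 3 | Direct to Visit 2 | In the gap of up to 14 days since the antecedent study | Does not apply | Ideation only | No |
| 4 | Direct to Visit 2 | During the antecedent study | Does not apply | Ideation only | No |
| 5 | Direct to Visit 2 | Earlier, but within 2 years | Does not apply | Ideation only | Not under this protocol |

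Reading the table:

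1. Cases 1 and 2 differ only in timing. The older attempt is excluded by rule and the more recent one is not.
2. Cases 1 and 5 can describe the same attempt. Only the entry route differs.
3. In cases 2 to 5, 2c would still exclude a subject who also answers yes to ideation item 4 or 5 for its reference period. The exclusion would then rest on the ideation and not on the attempt.
4. In cases 2 to 5 the opening clause and 2d remain available. Both are exclusion criteria, and Section 8.2 bars enrolment of anyone who fails a criterion. Both depend on the investigator's assessment.
5. 2a has the same route restriction as 2b, so the 6-month ideation look-back does not reach direct entrants under this protocol.

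The order of procedures is a separate check. At Visit 1, Section 10.2.1.1 makes the criteria review the last step, after the C-SSRS. At Visit 2, Section 10.2.2.1 puts the review first and gives the C-SSRS only to subjects already found eligible. As written, the input to 2c does not exist when the review that should apply 2c takes place.

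**The case against.** The strongest reply is that no suicidal subject goes unexamined.

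- The C-SSRS is done at Visit 2 on both routes and records behaviour. Note f to Table 2-1 requires an eligibility review at Visit 2 for everyone.
- Section 11 has reportable events recorded from consent, so an attempt between Visit 1 and Visit 2 has a second way of coming to light.
- For direct entrants, psychiatric history and the MINI are transcribed and updated if they have changed.
- An investigator who learns of a recent attempt has two binding grounds to exclude.
- Limiting 2a and 2b to Visit 1 attendees is explicit and identical in the synopsis and 8.2.2, so it is not a slip. The antecedent study may have applied the same look-backs weeks earlier.

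Much of this stands. Suicidality is assessed at Visit 2, so the gap is in how the result is used. The judgement clauses are real exclusions.

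Two parts do not answer the point. The protocol chose to set objective rules beside the judgement clauses for screened subjects, and it does not say why judgement alone suffices after screening or for direct entrants. Earlier screening, even if equivalent, cannot cover an attempt made during or after the antecedent study.

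**Conclusion.** The point holds in a limited form. The objective rules in exclusion 2 are uneven across entry routes and stop short of Visit 2 for suicidal behaviour. Separately, Section 10.2.2.1 orders the Visit 2 procedures so that 2c follows the review it should inform.

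For Visit 1 attendees the interval with no objective attempt rule is the 7 to 35 days between the visits. For direct entrants this protocol has no objective attempt criterion at all. The documents give no frequency. That few subjects would be affected is an assumption, but each case would be of high consequence.

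A reader might infer more than the documents support:

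- **That any attempt between the two studies escapes.** It does not. For a subject more than 14 days out, such an attempt precedes screening and 2b covers it if it falls within 2 years.
- **That nothing excludes the uncovered cases.** The opening clause and 2d bind on both routes. Different outcomes for the same history are therefore possible but not certain.
- **That every direct entrant goes unscreened for the full 2-year and 6-month look-backs.** The antecedent studies' criteria are not in these documents, so this can be neither confirmed nor ruled out.

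**What to change.** - Reconcile 2a, 2b and 2c with one another, in both 8.2.2 and the synopsis, so that it is clear what applies on each entry route and for the time up to Visit 2. If the differences are intended, state the reason.
- Bring the list of transcribed data in Section 10 into line with whatever 2a and 2b are meant to require of direct entrants.
- Correct the order in Section 10.2.2.1 so that the Visit 2 C-SSRS is available at the eligibility review.

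Which exclusion rule and which look-back apply is for the sponsor to decide.

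The cost is wording in the synopsis, 8.2.2, Section 10 and 10.2.2.1, plus transcription of existing data where the antecedent study collected it. The Visit 2 C-SSRS is already scheduled. Its since-last-visit form cannot supply a 6-month or 2-year history, so if the antecedent study holds no suitable record, a look-back for direct entrants would need another source. There may be a very small number of extra exclusions.

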### **8.3. Premature Subject Withdrawal**

All subjects will be advised that they are free to withdraw from participation in this study at any time, for any reason, and without prejudice. The Investigator should make every reasonable attempt to keep subjects in the study; however, subjects must be withdrawn from the study if they withdraw consent to participate. Investigators must attempt to contact subjects who fail to attend scheduled visits by telephone or other means to exclude the possibility of an AE being the cause of withdrawal. Should this be the cause, the AE must be documented, reported, and followed as described in Section 11.2.

The sponsor reserves the right to request the withdrawal of a subject due to protocol deviations or other reasons.

The Investigator also has the right to withdraw subjects from the study at any time for the following reasons:

- Withdrawal of informed consent (subject's decision to withdraw for any reason)
- Any AE, laboratory abnormality, positive pregnancy test, positive urine drug screen, any of the inclusion/exclusion criteria not met during the study or concomitant illness which, in the opinion of the Investigator, indicates that continued treatment with IP or any other aspect of the study is not in the best interest of the subject

Note: If central laboratory urine drug screen testing is positive for a subject after enrollment, then the participation of the subject in the study may have to be discontinued. The Medical Monitor should be consulted on these cases. An unscheduled repeat urine drug screen may be obtained to investigate whether drug use is continuing.

- Disease progression that, in the Investigator's opinion, precludes the subject's continued participation in the study
- Significant noncompliance with the requirements of the protocol or treatment
- Two consecutive missing visits and failure to contact the Investigator within a period of 2 weeks (during the Screening and Baseline visits) or 1 month (during treatment) with no reason for missing visit
- The subject requires use of a medication prohibited by the protocol. The Investigator should discuss these cases with the medical monitor before withdrawing the subject, to determine whether the subject can continue in the study or not.
- Termination of the study by VistaGen

- At the discretion of the Investigator or VistaGen
- Pregnancy

If a subject is withdrawn before completing the study, the reason for withdrawal and the date of discontinuation will be recorded on the appropriate page of the electronic case report form (eCRF).

All attempts will be made to have subjects return to the clinic to complete the assessments or procedures performed at the Early Termination visit (see Section 10.2.3) in the event of early withdrawal after Visit 2 or any visit other than Visit 14 after IP administration. All attempts to contact the subject, including phone or email, must be recorded in the source documents. Data will be collected from subjects on treatment only.

#### **8.4. Subject Replacement Criteria**

Withdrawn subjects will not be replaced. If a substantial number of subjects are withdrawn from the study, the sponsor will evaluate the need for developing replacement criteria. Rescreening will be permitted on a case-by-case basis after discussion with the medical monitor.

The subject number for a withdrawn subject will not be reassigned to another subject.

## 9. TREATMENTS

All IP should be refrigerated prior to use but administered only at room temperature.

Site personnel will instruct the subject to self-administer the IP by 1 spray into each nostril (right and left nasal passages), for 2 total sprays per dose.

### 9.1. Identification of Investigational Product

The IP (PH94B Nasal Spray) is supplied in a 10-mL amber glass vial with a spray actuator. The spray actuator has a clear protective cover.

PH94B is odorless and contains propylene glycol, ethyl alcohol, polysorbate 80, water (q.s. to 100%), and benzalkonium chloride as a preservative, in a phosphate buffer.

PH94B will be supplied in monthly kits consisting of a sufficient number of 10-mL amber glass vials, where each vial contains 8 mL of PH94B. Each metered dose spray delivers 1.6  $\mu$ g per 100  $\mu$ L spray. There is sufficient volume in each vial to deliver at least 60 sprays of PH94B.

Use of the i.n. route is essential given the site of action of PH94B on nasal sensory chemoreceptors (see Section 5.1).

PH94B will be supplied by [REDACTED]

New vials should be allowed to come to room temperature for 30 minutes and primed before use according to the instructions provided.

